10 STUDY DESIGN

International, multicentre, open-label proof of concept study without randomization and stratification. Two different dose groups are included. Group 1 consists of 10 patients that will receive 25E6 DCP-001 cells per vaccination with two additional booster vaccinations of 10E6 cells. Group 2 consists of 10 patients who will receive 50E6 DCP-001 cells per vaccination with two additional booster vaccinations of 10E6 cells.

11 STUDY POPULATION

11.1 NUMBER AND TYPE OF SUBJECTS

Twenty patients (male or female) with a confirmed diagnosis of AML that are in CR1 or CRi with MRD, greater than 18 years of age, will be enrolled in this study. Patients will be identified and invited to participate by the investigators at the respective study centres.

11.2 INCLUSION CRITERIA

Patients will be eligible for enrolment if the following criteria apply:

1. Confirmed diagnosis of AML according to WHO2016 criteria, including cytological, molecular and cytogenetic criteria (except acute promyelocytic leukaemia/APL).
2. In CR1 or CRi documented by bone marrow examination up to one month before vaccination; CR defined as less than 5% blasts in normo-cellular bone marrow, ANC $>1 \times 10^9/L$, platelet count $>100 \times 10^9/L$, no evidence of extra-medullary disease. Patients in CRi (patients with $<5\%$ blasts but with incomplete blood count recovery) should have platelets $>50 \times 10^9/L$.
3. MRD as defined by multicolour flow cytometry (MFC) at a value of $> 0.1\%$, or detection of specific molecular abnormalities such as NPM1 mutation
4. Patients that are in CR1 or CRi. Patients not having undergone consolidation therapy must have been in CR1 for at least 1 month prior to enrolment.
5. Expected to be willing and able to undergo all study procedures, including outpatient evaluations for clinical and immunological monitoring.
6. Male or female ≥ 18 years of age.
7. Women of childbearing potential must be using anti-conceptive therapy or use two (2) barrier contraceptive methods (one by each partner and at least one of the barrier methods and one must include spermicide, unless spermicide is not approved in the country or region). See section 12.8 for birth control methods deemed acceptable for this study
8. ECOG (WHO) performance status 0-2.
9. Willing and able to provide written informed consent for participation in the study.

11.3 MAIN EXCLUSION CRITERIA

1. APL (M3) type of AML.
2. Patients who have undergone or are scheduled/eligible for allogeneic stem cell transplantation.
3. History of previous allogeneic bone marrow or solid organ transplantation.
4. Uncontrolled or serious infections
5. Ongoing immunosuppressive therapy, other than short use of low dose steroids, i.e. equivalent to an average dose of $\leq 10\text{mg}$ of prednisone/day.
6. Chemotherapy and antineoplastic hormonal therapy within 28 days prior to the screening visit.
7. Active autoimmune disease.
8. Inadequate liver function (AST and ALT $> 3 \times \text{ULN}$, serum bilirubin $>3 \times \text{ULN}$).
9. Other active Malignancies within the last 5 years, except for adequately treated carcinoma in situ of the cervix or squamous carcinoma of the skin or adequately controlled limited basal cell skin cancer.
10. Pregnant or lactating females.

11. Major surgical procedure (including open biopsy) within 28 days prior to the first study treatment, or anticipation of the need for major surgery during the course of the study treatment.
12. Uncontrolled hypertension (systolic > 150 mm Hg and/or diastolic > 100 mm Hg) or clinically significant (i.e. active) cardiovascular disease.
13. Evidence of any other medical conditions (such as psychiatric illness, physical examination or laboratory findings that may interfere with the planned treatment, affect patient compliance or place the patient at high risk from treatment-related complications.
14. Known HIV, Hepatitis B and/or Hepatitis C infections.
15. History of hypersensitivity to the investigational medicinal product or to any excipient present in the pharmaceutical form of the investigational medicinal product.

11.4 DEFINITION OF SUBJECTS WHO ARE ENTERED INTO THE STUDY

A patient will be defined as having entered the study when he/she has signed/given informed consent. All entered patients will be assigned a subject number.

Patients who do not meet all the eligibility criteria will be considered as “screening failures”. The only screening data to be entered in the eCRF for all screening failure patients will be informed consent date, demographics, eligibility criteria and reason for discontinuation.

12 TREATMENTS TO BE ADMINISTERED

12.1 Study Drug

12.1.1 Investigational Product(s)

DCP-001 vaccine is presented as a direct injectable solution containing a mature dendritic cell preparation suspended in a cryopreservative, Cryostor™. The vaccine is gamma irradiated and packed in Daiko Crystal Zyneth break-resistant containers. The format is based on vials with a rubber stopper and aluminium crimp seal with flip off cap. The vaccine will be administered intradermal using a 1 mL syringe and a needle (Terumo, 21 GX 1 ½ ", 0.8 x 40mm). The needle and syringe required for injection purposes will be provided as part of the 'treatment pack'.

12.1.2 Comparative Drug(s)

Not Applicable

12.2 METHOD OF ASSIGNING SUBJECTS TO TREATMENT GROUPS

First 10 patients will receive the lowest dose (25E6cells/vaccination), the 2nd 10 patients will receive the high dose (50E6cells/vaccination).

12.3 DOSE LEVELS

Patients will receive 25E6 DCP-001 cells per vaccination (Group 1; 10 patients) or 50E6 DCP-001 cells (Group 2; 10 patients) per vaccination. Both groups will receive two additional booster vaccination of 10E6 cells.

The first treatment for both dose groups is given at Day 0 (Baseline), the second, third and fourth treatments are given at 2 weekly intervals. A total of 4 treatments will be administered in a 6 week timeframe followed by a booster vaccination at 8 and 12 weeks after the 4th vaccination at week 6. A summary of the treatment schedule is given below:

Groups 1 and 2;

Day 0 1st vaccination with 25E6 or 50E6 cells.

Week 2 2nd vaccination with 25E6 or 50E6 cells.

Week 4 3rd vaccination with 25E6 or 50E6 cells.

Week 6 4th vaccination with 25E6 or 50E6 cells.

Week 14 and 18 booster vaccination with 10E6 cells.

12.4 ROUTE OF ADMINISTRATION

Intradermal (i.d.) administration of the DCP-001 vaccine will be performed by an experienced and suitably trained nurse or physician. The first vaccine is given at Day 0. Two (25E6) or four (50E6) intradermal injections of 0,5 mL max into the upper left or right leg. The second, third and fourth DCP- 001 vaccinations are given at bi-weekly intervals, in close proximity to the first injections. A booster vaccination will be administered on Day 77 (visit 8) and Day 98 (visit 9).

After each vaccination, patients should be monitored for at least 60 minutes to exclude any immediate reactions to the intradermal administration.

Subjects can choose to alternate the leg the vaccine is administered in, or they can have the vaccine in the same leg throughout the study.

Training on vaccine administration and location of injections will be given to all study site members responsible for vaccine administration prior to the start of the study.

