2. Patients who have undergone or are scheduled for allogeneic stem cell transplantation.
3. History of previous allogeneic bone marrow or solid organ transplantation.
4. Uncontrolled or serious infections
5. Ongoing immunosuppressive therapy, other than short use of low dose steroids, i.e. equivalent to an average dose of $\leq 10\text{mg}$ of prednisone/day.
6. Chemotherapy and antineoplastic hormonal therapy within 28 days prior to the screening visits.
7. Active autoimmune disease.
8. Inadequate liver function (AST and ALT $> 3 \times \text{ULN}$, serum bilirubin $>3 \times \text{ULN}$).
9. Other active Malignancies within the last 5 years, except for adequately treated carcinoma in situ of the cervix or squamous carcinoma of the skin or adequately controlled limited basal cell skin cancer.
10. Pregnant or lactating females.
11. Major surgical procedure (including open biopsy) within 28 days prior to the first study treatment, or anticipation of the need for major surgery during the course of the study treatment.
12. Uncontrolled hypertension (systolic > 150 mm Hg and/or diastolic > 100 mm Hg) or clinically significant (i.e. active) cardiovascular disease.
13. Evidence of any other medical conditions (such as psychiatric illness, physical examination or

| |
|--|
| 
laboratory findings) that may interfere with the planned treatment, affect patient compliance or place the patient at high risk from treatment-related complications.
 
14. Known HIV, Hepatitis B and/or Hepatitis C infections.
 
15. History of hypersensitivity to the investigational medicinal product or to any excipient present in the pharmaceutical form of the investigational medicinal product.
 |
| 
Investigational product, dosage and mode of administration:
 
The investigational product is DCP-001, which consists of allogeneic human dendritic cells, expressing specific Leukaemia Associated Antigens (LAA) antigens.
 
Patients will receive either 25E6 (Group 1) or 50E6 (Group 2) DCP-001 cells/vaccination. Both groups will receive a total of 4 vaccinations at biweekly intervals (weeks 0, 2, 4 and 6) followed by 2 booster vaccinations 8 and 12 weeks after the 4th (week 6) vaccination of 10E6 cells. DCP-001 will be applied intra-dermally (2-4 injections per vaccination, 1 per booster vaccination) and is formulated as a direct injectable vaccine.
 |

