7 FLOW CHART AND SCHEDULE OF ASSESSMENTS

Table 1: Flowchart and assessment schedule

| | Screening | Baseline wk 0 | wk 0 | wk 2 | wk 4 | wk 6 | wk 6 | wk 11 | wk 14 | wk 18 | wk 18 | wk 20 | wk 32 | FU ¹ +8 weeks | End of Study ² (Final FU Visit) |
|--|-----------|--------------------|----------------|-----------------|-----------------|-----------------|-----------------|-----------------|-----------------|------------------|------------------|------------------|------------------|--------------------------------|---|
| days | -28 | 0 | 2 ⁷ | 14 ⁸ | 28 ⁸ | 42 ⁸ | 44 ⁷ | 77 ⁸ | 98 ⁸ | 126 ⁸ | 128 ⁷ | 140 ⁸ | 224 ⁸ | | |
| Visit No. | 1 | 2 | 3 | 4 | 5 | 6 | 7 | 8 | 9 | 10 | 11 | 12 | 13 | 14-17 | 18 |
| Informed consent | √ | | | | | | | | | | | | | | |
| Inclusion/exclusion criteria | √ | | | | | | | | | | | | | | |
| Demographics | √ | | | | | | | | | | | | | | |
| Medical History | √ | | | | | | | | | | | | | | |
| Physical examination | √ | √ | | √ | √ | √ | | √ | √ | √ | | √ | √ | √ | √ |
| ECOG | √ | √ | | √ | √ | √ | | √ | √ | √ | | √ | √ | √ | √ |
| HLA Typing ¹¹ | √ | | | | | | | | | | | | | | |
| Vital signs | √ | √ ³ | | √ | √ | √ | | √ | √ | √ | | √ | √ | √ | √ |
| ECG, X-thorax | √ | | | | | | | | | | | | | | |
| Haematology ⁴ | √ | √ ³ | | √ | √ | √ | | | √ | √ | | √ | √ | √ | √ |
| Biochemistry ^{5, 13} | √ | √ ^{3, 13} | | √ | √ | √ | | | √ | √ | | √ | √ | √ | √ |
| Urine analysis ¹⁰ | √ | | | | | | | | | | | | | | √ |
| Viral tests (HIV, Hepatitis B and C) ¹² | √ | | | | | | | | | | | | | | |
| MRD assessment (BM aspirate) | | √ | | | | | | | √ | | | √ | √ | | |
| DCP-001 Vaccination | | √ | | √ | √ | √ | | | √ | √ | | | | | |
| Immunomonitoring | | √ | √ | | | | √ | √ | | | √ | √ | √ | | |
| Skin biopsy ⁹ | | | √ | | | | √ | | | | √ | | | | |
| End of treatment | | | | | | | | | | | | | √ | | |
| End of study | | | | | | | | | | | | | | | √ |
| Prior and Concomitant medication | √ | √ | √ | √ | √ | √ | √ | √ | √ | √ | √ | √ | √ | √ | √ |
| Adverse event reporting ⁶ | | √ | √ | √ | √ | √ | √ | √ | √ | √ | √ | √ | √ | √ | √ |

- 1) Follow up visits on wk 40, 48 and 56
- 2) End of study visit (last FU visit) will be performed 12 months after 4th vaccination, or, no more than 2 weeks after last treatment received if a patient goes off study before week 32
- 3) If baseline assessment is within 7 days of first vaccination and if results meet the stated eligibility criteria, these assessments need not to be repeated on day 0

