8.10.4 BLOOD, BONE MARROW AND SKIN BIOPSY SAMPLING

This study involves frequent blood and bone marrow sampling. The total number and volume of blood samples is detailed in Table 4.

For immunomonitoring purposes, 70 mL of blood will be collected in heparin coated tubes. Samples will be taken at screening, start vaccination (d=0), day 44, day 77, day 128, day 140 and day 224.

For hematology diagnostic purposes, 21 mL of blood will be collected in heparin coated tubes.

Bone marrow aspirates (at least 3 ml or 16.106 cells for LAP analysis and 10 ml for biobanking) will be collected in heparin coated tubes. Samples will be taken at baseline (d=0), day 98, day 140, and at day 224. All BM samples should be obtained preferably from the first tap, gathered in heparin-coated tubes and kept at room temperature. In any case it should be indicated whether the sample is from the first or second tap. In addition, a single skin biopsy will be taken at 48h post 1st vaccination, 4th vaccination and 2nd booster vaccination. The biopsy will be 4-6 mm and will be taken using a standard punch needle. The injection site to be biopsied will be chosen at random and an injection site will be used for biopsy only once (no repeat biopsy of any injection site).

Table 4: Invasive procedures and sample sizes

| Visit no. | 1 | 2 | 3 | 4 | 5 | 6 | 7 | 8 | 9 | 10 | 11 | 12 | 13 |
|---|----|-----|----|-----|-----|-----|----|----|-----|-----|-----|-----|-----|
| Day | | 0 | 2 | 14 | 28 | 42 | 44 | 77 | 98 | 126 | 128 | 140 | 224 |
| quantity of Blood (mL) | | | | | | | | | | | | | |
| For diagnosis | 21 | 21 | | 21 | 21 | 21 | | | 21 | 21 | | 21 | 21 |
| For HLA classification | 24 | | | | | | | | | | | | |
| For immunomonitoring | | 70 | 70 | | | | 70 | 70 | | | 70 | 70 | 70 |
| quantity of Bone Marrow aspirate (mL) | | | | | | | | | | | | | |
| for diagnosis | | > 3 | | | | | | | > 3 | | | > 3 | > 3 |
| For biobank | | 10 | | | | | | | 10 | | | 10 | 10 |
| Vaccination | | | | | | | | | | | | | |
| number of intradermal injections ¹ | | 2-4 | | 2-4 | 2-4 | 2-4 | | | 1 | 1 | | | |
| Skin test | | | | | | | | | | | | | |
| number of biopsies ² | | | 1 | | | | 1 | | | | 1 | | |

1) Depending on dose: 2 for low dose, 4 for high dose and 1 for boosting dose

2) 1 biopsy to be taken from 1 injection site

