- Skin biopsy from 1 out of the 2 or 4 injection sites for evaluation of immunological response in skin biopsy.
- Blood sample collection for immunological response
- Record any AEs, SAEs and concomitant medications and/or changes in ongoing AEs, SAEs and ongoing concomitant medications
- Day is fixed with the previous visit (Visit 6)

Treatment Period (Visit 8)/ day 77

according to the assessment schedule \pm 3 days

- Physical examination, ECOG and Vital signs
- Record any new AEs, SAEs and concomitant medications and/or changes in ongoing AEs, SAEs and ongoing concomitant medications
- Blood sample collection for immunological response

Treatment Period (Visit 9-10)/days 98, 126

according to the assessment schedule \pm 3 days

- Physical examination, ECOG and Vital signs
- Hematology and biochemistry
- Record any new AEs, SAEs and concomitant medications and/or changes in ongoing AEs, SAEs and ongoing concomitant medications.
- Administration of study medication (DCP-001 booster vaccination)
- **Visit 9;** Bone marrow aspirate for MRD analysis (MRD assessment) and biobanking

Treatment Period (Visit 11)/day 128

- Skin biopsy from 1 out of the 2 or 4 injection sites for evaluation of immunological response in skin biopsy
- Blood sample collection for immunological response (immunomonitoring)
- Record any new AEs, SAEs and concomitant medications and/or changes in ongoing AEs, SAEs and ongoing concomitant medications
- Day is fixed with the previous visit (visit 10)

Treatment Period (Visit 12)/day 140

according to the assessment schedule \pm 3 days

- Physical examination, ECOG and Vital signs
- Hematology and biochemistry
- Record any AEs, SAEs and concomitant medications and/or changes in ongoing AEs, SAEs and ongoing concomitant medications.
- Bone marrow aspirate for MRD analysis (MRD assessment) and biobanking
- Blood sample collection for immunological response (immunomonitoring)

Treatment Period (Visit 13)/ day 224

according to the assessment schedule \pm 3 days

- Physical examination, ECOG and Vital signs
- Hematology and biochemistry
- Record any new AEs, SAEs and concomitant medications and/or changes in ongoing AEs, SAEs and ongoing concomitant medications.
- Bone marrow aspirate for MRD analysis (MRD assessment) and biobanking
- Blood sample collection for immunological response

Follow-up visits (14-17)

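### Section 12.4 gives the booster days as Day 77 (visit 8) and Day 98 (visit 9), but everywhere else the protocol times them they fall on Day 98 (visit 9) and Day 126 (visit 10)

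*Protocol*

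**What the plan says.** Section 12.4 (Route of Administration) reads: "A booster vaccination will be administered on Day 77 (visit 8) and Day 98 (visit 9").

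The rest of the protocol gives a different schedule:

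- **Synopsis, dosage entry:** "followed by 2 booster vaccinations 8 and 12 weeks after the 4th (week 6) vaccination of 10E6 cells". The duration entry repeats the 8 and 12 weeks and sets total treatment at 18 weeks.
- **Section 12.3, directly before 12.4:** "Week 14 and 18 booster vaccination with 10E6 cells".
- **Section 14.1:** the booster is listed under "Treatment Period (Visit 9-10)/days 98, 126". The entry headed "Treatment Period (Visit 8)/ day 77" lists an examination, recording of adverse events and medication, and a blood sample for immune monitoring, but no study drug.
- **Table 1:** the row "DCP-001 Vaccination" is ticked at Days 0, 14, 28, 42, 98 and 126, and is blank at Day 77.
- **Table 4:** one injection each at Days 98 and 126, none at Day 77.

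Two sampling rules also depend on the booster dates. The synopsis places one MRD assessment before the first boost and the final one, on Day 224, 100 days after the last. Section 8.10.4 states: "In addition, a single skin biopsy will be taken at 48h post 1st vaccination, 4th vaccination and 2nd booster vaccination". The third biopsy belongs to visit 11 (Day 128), for which section 14.1 says: "Day is fixed with the previous visit (visit 10").

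**The concern.** Section 12 holds the dosing instructions. Within it, 12.3 gives the boosters in weeks only, so 12.4 is the one place there that names a study day and visit number for them, and as a schedule it is wrong. The error can be carried out: visit 8 is a real visit with the patient present. It is also a visit without haematology or biochemistry, which are scheduled at every visit where the protocol intends a vaccination.

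What is at stake is the meaning of the later samples. MRD and immune response are two of the three primary objectives, and both are summarised by group and visit. If the boosters move and the sampling days do not, the same visit label covers different intervals since the last dose in different patients. The samples concerned are the Day 98, 140 and 224 marrows, the third skin biopsy and the blood samples from Day 128 on. The Day 77 blood sample could also be affected, because section 14.1 sets no pre-dose order at a visit where no dose is expected.

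**Working it through.** **Inputs.** Fourth vaccination at week 6, Day 42 (section 12.3, Table 1). Boosters 8 and 12 weeks later (synopsis, section 12.3). Booster days in section 12.4: 77 and 98. Sampling days 98, 128, 140 and 224 (Tables 1 and 4). Visit window ±3 days (Table 1, footnote 8).

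**Step 1. Booster days from the stated intervals.**
- First: 42 + 8 × 7 = 98, which is week 14.
- Second: 42 + 12 × 7 = 126, which is week 18.

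These match the days and visits in Table 1, Table 4 and section 14.1, and the 18-week treatment duration.

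**Step 2. Intervals implied by section 12.4.**
- First: (77 − 42)/7 = 5 weeks after the fourth vaccination.
- Second: (98 − 42)/7 = 8 weeks after it.

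Section 12.4 does not reproduce the 8 and 12 weeks. Its last dose falls at 98/7 = week 14, not week 18.

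**Step 3. Independent check on the last boost.** The final MRD assessment on Day 224 is described as 100 days after the last boost.
- Last boost on Day 126: 224 − 126 = 98 days, in agreement.
- Last boost on Day 98: 224 − 98 = 126 days, not in agreement.

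The Day 128 biopsy gives the same answer: 128 − 126 = 2 days, the required 48 hours, against 128 − 98 = 30 days.

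**Step 4. Size of the shift.** Booster 1 is 98 − 77 = 21 days early and booster 2 is 126 − 98 = 28 days early, both well outside ±3 days.

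**Step 5. Effect on sample timing if a site doses by 12.4 and samples by Table 1.**

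| Sample | Measured from | Intended | Under 12.4 |
|---|---|---|---|
| Day 98 marrow | booster 1 | same day, before the dose | 98 − 77 = 21 days after |
| Day 128 biopsy and blood | booster 2 | 128 − 126 = 2 days | 128 − 98 = 30 days |
| Day 140 marrow | booster 2 | 140 − 126 = 14 days | 140 − 98 = 42 days |
| Day 224 marrow | booster 2 | 224 − 126 = 98 days | 224 − 98 = 126 days |

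With 10 patients per group, one such patient is 1/10 = 10% of the values at each of these visits.

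**The case against.** The strongest reply is that the slip corrects itself. The right weeks stand in the section immediately before, the visit-by-visit instructions and both tables agree with them, and section 14.1 sends sites to Table 1 for procedures. Administration training, a pharmacy manual, monitoring and eCRF recording of the quantity given make a wrong dose less likely or easier to detect. The intervals in the table above also need a site to dose by 12.4 while sampling by documents that contradict it. Such a patient would reach visit 10 with another booster listed, and the conflict would probably surface then.

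Much of this stands. The intended schedule is not in doubt, so this is an internal contradiction and not a poor design choice. The 10% figure is a share of the data, not an estimate of bias, and because the analysis is descriptive no test or decision rule is affected. Some places that mention the boosters (sections 10 and 16.3) give no date, and the synopsis and 12.3 give weeks that have to be converted. The support from the third biopsy is also less tidy than it might be: the synopsis and Table 1 footnote 9 name only the biopsies after the first and fourth vaccinations, although Table 1 ticks Day 128 and section 8.10.4 includes the third.

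None of this makes the sentence right. By the time visit 10 exposes the conflict, both boosters have been given on the wrong days and the Day 98 marrow is no longer a pre-boost sample. The safeguards may catch the error; they do not remove it from the text.

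**Conclusion.** The concern holds. Section 12.4 is wrong as written, and every part of the protocol that times the boosters contradicts it. The correct days are Day 98 (visit 9) and Day 126 (visit 10); 12.4 is early by 21 and 28 days.

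The error is certain; its effect on the data is conditional. The protocol does not show that anyone was boosted on Day 77, and the changed sample intervals assume dosing by 12.4 with sampling on the scheduled days. Samples before Day 77 are unaffected. So is the treatment-emergent adverse event rule in section 16.2.4, which runs to 30 days after the actual last vaccination. It should be fixed: it is a wrong dosing day in an operative instruction, and it bears on samples that serve two primary objectives.

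**What to change.** Replace the sentence in section 12.4 with: a booster vaccination will be administered on Day 98 (visit 9) and Day 126 (visit 10). Notify the sites in writing.

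Then check the dosing dates recorded in the eCRF. If any patient was boosted on Day 77, flag that patient in the by-visit MRD and immune summaries and give the actual days since the last boost. The flagging can go in the statistical analysis plan and is needed only if such a patient is found.

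The cost is one sentence in a protocol clarification, a site letter and a check of recorded dates. No patients, visits or procedures are added.
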